11.0 Study Management

11.1 Subject Data Protection

In accordance with the Health Information Portability and Accountability Act (HIPAA), subjects who have provided written informed consent must also sign a subject authorization to release medical information to the study Sponsor and allow a regulatory authority, or Institutional Review Board access to subject's medical information relevant to the study.

11.2 Data and Safety Monitoring

In addition to adverse event monitoring and clinical oversight by the Study Chair, site principal investigator and co-investigators, quality assurance of the study will be performed by the clinical trials office internal monitor. Monitoring frequency will be after 7 patients (part 1 of the trial) and then annually.

This study will also use the UCSD Moores Cancer Center Data Safety and Monitoring Board (DSMB) to

provide oversight in the event that this treatment approach leads to unforeseen toxicities. Data from this study will be reported every year, and will include:

- 1) the protocol title, IRB protocol number, and the activation date of the study.
- 2) the number of patients enrolled to date
- 3) the date of first and most recent patient enrollment
- 4) a summary of all adverse events regardless of grade and attribution
- 5) a response evaluation for evaluable patients when available
- a summary of any recent literature that may affect the ethics of the study.

11.3 Record Retention

Study documentation includes all Case Report Forms, data correction forms or queries, source documents, Sponsor-Investigator correspondence, monitoring logs/letters, and regulatory documents (e.g., protocol and amendments, IRB correspondence and approval, signed patient consent forms).

Source documents include all recordings of observations or notations of clinical activities and all reports and records necessary for the evaluation and reconstruction of the clinical research study.

Study documents should be kept on file until three years after the completion and final study report of this investigational study.

11.4 Obligations of Investigators

The Principal Investigator is responsible for the conduct of the clinical trial at the site in accordance with Title 21 of the Code of Federal Regulations and/or the Declaration of Helsinki. The Principal Investigator is responsible for personally overseeing the treatment of all study patients. The Principal Investigator must assure that all study site personnel, including sub-investigators and other study staff members, adhere to the study protocol and all FDA/GCP/NCI regulations and guidelines regarding clinical trials both during and after study completion.

13.0 Appendices

Appendix A: ECOG Performance Status

GRADE ECOG PERFORMANCE STATUS

Fully active, able to carry on all pre-disease performance without restriction

Restricted in physically strenuous activity but ambulatory and able to carry out work of a light or sedentary nature, e.g., light house work, office work

Ambulatory and capable of all selfcare but unable to carry out any work activities; up and about more than 50% of waking hours

Capable of only limited selfcare; confined to bed or chair more than 50% of waking hours

Completely disabled; cannot carry on any selfcare; totally confined to bed or chair

Appendix B: Tumor Lysis Syndrome Definitions

Cairo-Bishop Clinical Tumor Lysis Syndrome Definition and Grading

	Grade					
Complication	0	1	2	3	4	5
Creatinine*,†	≤ 1.5 × ULN	1.5 × ULN	$1.5 - 3.0 \times ULN$	> 3.0 - 6.0 × ULN	> 6.0 × ULN	Death
Cardiac Arrhythmia*	None	Intervent ion not indicated	Non-urgent medical intervention indicated	Symptomatic and incompletely controlled medically or controlled with device (e.g., defibrillator)	Life- threatening (e.g., arrhythmia associated with CHF, hypotension, syncope, shock)	Death
Seizure*	None		One brief, generalized seizure; seizure(s) well controlled by anticonvulsants or infrequent focal motor seizures not interfering with ADL		Seizure of any kind which are prolonged, repetitive or difficult to control (e.g., status epilepticus, intractable epilepsy)	Death

ULN = upper limit of normal; CHF = congestive heart failure; ADL = activities of daily living

Note: Laboratory tumor lysis syndrome and at least one clinical complication.

Cairo-Bishop Definition of Laboratory Tumor Lysis Syndrome

This definition comprises ≥ 2 of the following metabolic abnormalities occurring within 7 days from first dose at initial dosing or at dose escalation.

Element	Value	Change from Baseline
Uric Acid	\geq 476 μ mol/L or 8 mg/dL	25% increase
Potassium	\geq 6.0 mmol/L or 6 mEq/L	25% increase
Inorganic Phosphorus	$\geq 1.45 \text{ mmol/L}$	25% increase
Calcium	$\leq 1.75 \text{ mmol/L}$	25% decrease

^{*} Not directly or probably attributable to therapeutic agent.

[†] If no institutional ULN is specified, age/sex ULN creatinine may be defined as follows: Cairo-Bishop Clinical Tumor Lysis Syndrome Definition and Grading.

Howard Definition of Laboratory Tumor Lysis Syndrome

This definition comprises ≥ 2 of the following metabolic abnormalities.

Element	Value
Uric Acid	≥ 476 µmol/L or 8 mg/dL
Potassium	≥ 6.0 mmol/L or 6 mEq/L
Inorganic Phosphorus	≥ 1.45 mmol/L
Calcium	≤ 1.75 mmol/L

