- 10. Adequate renal function: Creatinine clearance based on 24 hr collection >/= 40 ml/min; OR Calculated Creatinine clearance (CrCl) ≥ 40 mL/min (based upon the Cockcroft-Gault Equation [CrCl = (140-age) * actual wt (in kg) * (0.85 if female) / (72 * Cr)].
- 11. Adequate hepatic function per local laboratory reference range as follows:
 - a. Aspartate transaminase (AST) and alanine transaminase (ALT) < 3.0X ULN
 - b. Bilirubin ≤1.5 x ULN (unless bilirubin rise is due to Gilbert's syndrome or of non-hepatic origin)

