	2 nd and subsequent occurrence	Interrupt venetoclax. Consider using G-CSF as clinically indicated. Follow dose reduction guidelines in Table 5 when resuming treatment with venetoclax after resolution. Additional dose reductions may occur at the discretion of the physician.	

Consider discontinuing venetoclax for subjects who require dose reductions to less than 100 mg for more than 2 weeks.

Management of Neutropenia

Based on clinical observations with the 1st generation Bcl-2 inhibitor, navitoclax and in vitro colony-forming assays to assess Bcl-2-selective inhibitor effects on granulocyte precursors, it is possible that subjects treated with venetoclax might experience neutropenia. Subjects with a history of neutropenia, who have received multiple prior therapies and/or have significant bone marrow involvement, may be at particular high risk. If determined to be clinically indicated by the treating physician in compliance with ASCO guidelines, G-CSF may be administered during dosing of venetoclax. The use of G-CSF support is strongly recommended for subjects with Grade 4 neutropenia (ANC < $500/\mu$ L). If the subject presents with febrile neutropenia or Grade 4 neutropenia for more than one week despite the use of optimal G-CSF support, venetoclax dosing should be interrupted until ANC recovery to > $500/\mu$ L. Venetoclax may then be re-initiated at a

Adverse reactions were graded using NCI CTCAE version 4.03.

b. Clinical TLS was defined as laboratory TLS with clinical consequences such as acute renal failure, cardiac arrhythmias, or sudden death and/or seizures.

lower dose as defined in the following table. Subjects not responding to G-CSF despite venetoclax interruption should undergo further evaluation to determine the etiology of the neutropenia.

Table 5. Dose Modification for Toxicity during Venetoclax Treatment.

Venetoclax Dose	Reduced Dose	
400 mg	300 mg	
300 mg	200 mg	
200 mg	100 mg	
100 mg	50 mg	
50 mg	Re-challenge at 20 mg ^a	

a. Subjects who do not tolerate 20 mg will discontinue venetoclax, but may remain on study to assess for progression.

Management of Lymphopenia

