9.0 Statistical Considerations

9.1 General Considerations

This is a pilot/feasibility clinical trial, with the primary feasibility endpoint being debulking of tumor burden to meet criteria for low Tumor Burden upon the completion of cycle 0

.The primary efficacy endpoint is the percentage of patients that have a decrease in tumor burden from levels of disease that meet "Medium/High-tumor burden" criteria to "Low tumor burden" criteria for disease burden following a maximum of 2 cycles of HDMP + Rituximab (called cycle 0 in the protocol schedule of events).

Tumor burden will be assessed prior to initiation of therapy, and after each cycle of HDMP + Rituximab (maximum 2 cycles). See section 8.1 for the definition of these categories of tumor burden.

The secondary endpoints are as follows:

- Percentage of patients that have a decrease in tumor burden from levels of disease that meet "Medium/High-tumor burden" to meet "Low tumor burden" criteria for disease burden following 1 cycle of HDMP + Rituximab.
- Percentage of patients that have a decrease in tumor burden from levels of disease that meet "Medium/High-tumor burden" to meet "Low tumor burden" criteria for disease burden following 2 cycles of HDMP + Rituximab.
- Rate of laboratory TLS (from start of treatment until completion of venetoclax ramp-up).
 See Appendix B for definition and grading of TLS.
- Rate of clinical TLS (from start of treatment until completion of venetoclax ramp-up)

- Adverse events by CTCAE4 definitions and iwCLL definition for hematologic AEs (see section 10.0 for iwCLL definition of hematologic AE).
- Overall Response rate (ORR), Partial Response (PR) rate, and Complete response (CR) rate per iwCLL criteria after 9 months of venetoclax and at completion of treatment. See section 8.2 for iwCLL criteria for definitions of each level of response. ORR includes all patients who have either a PR or CR.
- Undetectable minimal residual disease (MRD) rate based on bone marrow biopsy after 9
 months of venetoclax, and at completion of treatment. Undetectable MRD is defined as
 less than 0.01% CLL cells.

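### The clinical TLS endpoint counts creatinine above about 1.5 × ULN without requiring a rise, so some eligible patients can meet the complication before any dose

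*Combined protocol and SAP*

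**What the plan says.** The rate of clinical TLS, from start of treatment to the end of venetoclax ramp-up, is a secondary endpoint (sections 3.0 and 9.1). Under the laboratory TLS endpoint, section 9.1 adds: "See Appendix B for definition and grading of TLS".

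Appendix B builds clinical TLS from two parts: "Note: Laboratory tumor lysis syndrome and at least one clinical complication". The complications are creatinine, arrhythmia and seizure. Creatinine is graded only against ULN: grade 0 up to 1.5 × ULN, grade 2 from 1.5 to 3.0 × ULN, grade 3 above 3.0 × ULN. The one qualifier relevant here is the asterisk: "Not directly or probably attributable to therapeutic agent". The Cairo-Bishop laboratory table in the same appendix does carry a change-from-baseline column, for "metabolic abnormalities occurring within 7 days from first dose at initial dosing or at dose escalation"; the creatinine row has no counterpart.

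On renal entry, section 5.1 requires "Creatinine clearance based on 24 hr collection >/= 40 ml/min; OR Calculated Creatinine clearance (CrCl) ≥ 40 mL/min". It sets no limit on serum creatinine.

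A second wording stands in the footnote to Table 4 (section 7.3.4): "Clinical TLS was defined as laboratory TLS with clinical consequences such as acute renal failure, cardiac arrhythmias, or sudden death and/or seizures".

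**The concern.** An endpoint meant to capture harm from tumor lysis should not be reachable through a value that was present before treatment and has not changed. Under Appendix B as written, a patient whose stable creatinine is already above 1.5 × ULN carries the clinical component from day 1. If that patient then has laboratory TLS, the event is recorded as clinical TLS although nothing clinical has happened.

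Lowering TLS risk is the reason for the trial, so readers will look at this rate closely. With 17 patients, one reclassified event is visible. The Table 4 footnote names an acute renal event, so the same patient may be labelled differently in the two places.

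**Working it through.** The plan states no figure on this point, so there is nothing to reproduce. The check asks whether an eligible patient can sit above 1.5 × ULN at entry, and what one such case does to the rate.

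**Inputs from the documents.** The CrCl floor is 40 mL/min and the formula is "CrCl = (140-age) * actual wt (in kg) * (0.85 if female) / (72 * Cr") (section 5.1). The creatinine threshold is 1.5 × ULN (Appendix B). The sample size is 17 (section 9.2).

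**Assumptions.** The documents give no ULN. I took 1.2–1.35 mg/dL for men and 1.0–1.2 mg/dL for women. They give no renal, age or weight distribution either, so the patient profiles are illustrations. The inversion applies to the calculated-clearance route, not to a 24-hour collection.

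**Step 1: creatinine implied at CrCl 40.** Cr = (140 − age) × weight × (0.85 if female) / (72 × 40), where 72 × 40 = 2880. The break-even ULN is Cr / 1.5; the complication is met at entry when the local ULN is below it.

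| Profile | Calculation | Cr (mg/dL) | Multiple of assumed ULN | Break-even ULN | Met at entry? |
|---|---|---|---|---|---|
| Man 60 y, 90 kg | 80 × 90 / 2880 | 2.50 | 1.85–2.08 | 1.67 | Yes |
| Man 65 y, 80 kg | 75 × 80 / 2880 | 2.08 | 1.54–1.74 | 1.39 | Yes |
| Man 70 y, 80 kg | 70 × 80 / 2880 | 1.94 | 1.44–1.62 | 1.30 | Depends on ULN |
| Man 75 y, 70 kg | 65 × 70 / 2880 | 1.58 | 1.17–1.32 | 1.05 | No |
| Woman 60 y, 90 kg | 0.85 × 80 × 90 / 2880 | 2.12 | 1.77–2.12 | 1.42 | Yes |
| Woman 70 y, 70 kg | 0.85 × 70 × 70 / 2880 | 1.45 | 1.21–1.45 | 0.96 | No |

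**Step 2: how this depends on clearance.** The grid is age 50–85 by 5 years and weight 50–110 kg by 10 kg, which gives 56 unweighted cells per sex. Cells above 1.5 × ULN across the assumed ULN range:

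| CrCl (mL/min) | Men | Women |
|---|---|---|
| 40 | 27–34 of 56 | 22–35 of 56 |
| 50 | 11–19 | 10–20 |
| 60 | 4–8 | 2–10 |
| 70 | 0–2 | 0–3 |
| 80 | 0 | 0 |

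The overlap is not confined to the floor. For a man of 60 years and 90 kg with ULN 1.2, the threshold of 1.80 mg/dL is reached at CrCl 80 × 90 / (72 × 1.80) = 55.6 mL/min. Cell counts are not patient proportions.

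**Step 3: effect on the endpoint.** Clopper-Pearson 95% intervals:

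- 0/17 = 0% (0–19.5%)
- 1/17 = 5.9% (0.1–28.7%)
- 2/17 = 11.8% (1.5–36.4%)

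**Step 4: would a grade shift repair it?** Grade 2 runs from 1.5 to 3.0 × ULN. With ULN 1.2–1.3, the upper edge is 3.6–3.9 mg/dL. A patient starting at 2.08 could rise by 73–87% (3.6 / 2.08 = 1.73; 3.9 / 2.08 = 1.87) without changing grade. A change threshold does better: 0.3 mg/dL is reached at 2.38 and 25% at 2.60.

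**The case against.** **Laboratory TLS is still needed.** This stands. Renal impairment alone is never an event; the patient must first have at least two metabolic abnormalities.

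**Low clearance does not imply high creatinine.** This stands too. A reader might infer that any stable renal impairment, or any patient near CrCl 40, turns laboratory TLS into clinical TLS. The documents do not support that: older or lighter patients at CrCl 40 can be below 1.5 × ULN, and no grid cell exceeds it at CrCl 80.

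**Context excludes unchanged values.** The column is headed as complications, the endpoint runs from start of treatment, and section 10.0 defines treatment-emergent events by onset or worsening. A sensible assessor might ignore a stable value. But the section 10.0 wording governs adverse events, while section 9.1 sends TLS to Appendix B, whose asterisk removes only drug-attributable complications.

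**The importance is limited.** Section 9.2 reports safety descriptively and did not size the trial for it, and section 4.3 explains why the TLS rate is not primary. It is tempting to set 5.9% against the 3.1% in section 2.2.3.3, but that figure is grade 3 or 4 TLS. A stable creatinine of 1.5–3.0 × ULN is grade 2 in Appendix B, so the two are not comparable.

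**Table 4 does not contradict Appendix B outright.** A reader might say that the footnote requires acute renal failure. It does not; the list is illustrative. The wordings still differ, because its renal example is acute and Appendix B asks for no change.

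**Appendix B is a named standard.** A trial-specific variant costs comparability, which is why both counts should be reported.

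**Conclusion.** The concern holds in a limited form. The stated rule can label an unchanged baseline creatinine as the clinical component of TLS, and the entry criteria admit patients to whom this applies. It affects only patients whose stable creatinine already exceeds about 1.5 × ULN and who also develop laboratory TLS. How many there will be cannot be derived from the documents, and it may be none. Each one adds 1/17, or 5.9 percentage points, to a descriptive secondary rate.

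The existence of such patients rests on the protocol's own formula plus an assumed ULN range. The heavier profiles in the table qualify at any ULN in that range, so the conclusion does not hang on one choice. The primary endpoint, sample size and stopping rule are unaffected. The change is worth making because it is cheap and removes a foreseeable misclassification in the trial's most relevant safety outcome.

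**What to change.** For the endpoint only, add a sentence to Appendix B and refer to it in section 9.1: the creatinine complication counts when creatinine is above 1.5 × ULN **and** has risen from the pre-treatment value (baseline as in section 9.5) or the pre-dose value of that dose step. Allowing either reference keeps a cumulative rise across ramp-up from being missed.

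Take the size of the rise from thresholds already in Appendix E: at least 0.3 mg/dL from pre-dose (hyperuricemia row) or at least 25% from baseline (creatinine row). Name the choice before the analysis. Do not use a grade shift, for the reason in step 4. Report the unmodified Cairo-Bishop count beside the modified one.

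The cost is small. Creatinine is part of the metabolic panel already scheduled in Cycle 0 and at each ramp-up step, so no procedure is added. The downsides are a trial-specific variant of a standard definition and one extra tabulation.

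Separately, Table 4 attaches a venetoclax restart instruction to the clinical TLS label. The sponsor must reconcile its footnote with Appendix B and say which definition applies where. No dosing rule is proposed here.

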Appendix C. Sample List of Excluded and Cautionary Medications

Excluded during ramp-up phase and Cautionary at the Cohort Designated Dose:

Strong CYP3A inducers - avasimibe, carbamazepine, enzalutamine, mitotane, phenytoin, rifampin, St. John's wort

Moderate CYP3A inducers - bosentan, efavirenz, etravirine, modafinil, nafcillin

Strong CYP3A inhibitors - boceprevir, clarithromycin, cobicistat, conivaptan, danoprevir/ritonavir, elvitegravir/ritonavir, idelalisib,* indinavir, itraconazole, ketoconazole, mibefradil, lopinavir/ritonavir, nefazodone, nelfinavir, ritonavir, paritaprevir/ritonavir combinations, posaconazole, saquinavir, telaprevir, telithromycin, tipranavir/ritonavir, voriconazole

Moderate CYP3A inhibitors - amprenavir, aprepitant, atazanavir, cimetidine, ciprofloxacin, clotrimazole, crizotinib*, cyclosporine*, darunavir/ritonavir, diltiazem¹, erythromycin, fluconazole, fosamprenavir, imatinib*, isavuconazole, tofisopam, verapamil

Cautionary

Warfarin**

P-gp substrates

Aliskiren, ambrisentan, colchicine, dabigatran etexilate, digoxin, everolimus*, fexofenadine, lapatinib*, loperamide, maraviroc, nilotinib*, ranolazine, saxagliptin, sirolimus*, sitagliptin, talinolol, tolvaptan, topotecan*

BCRP substrates

Methotrexate*, mitoxantrone*, irrinotecan*, lapatinib*, rosuvastatin, sulfasalazine, topotecan*

OATP1B1/1B3 substrates

Atrasentan, atorvastatin, ezetimibe, fluvastatin, glyburide, rosuvastatin, simvastatin acid, pitavastatin, pravastatin, repaglinide, telmisartan, valsartan, olmesartan

P-gp inhibitors

Amiodarone, captopril, carvedilol, dronedarone, felodipine, quercetin, quinidine, ronalzine, ticagrelor

BCRP inhibitors

Geftinib*

Note that this is not an exhaustive list. For an updated list, see the following link:

http://www.fda.gov/Drugs/DevelopmentApprovalProcess/DevelopmentResources/DrugInteractions Labeling/ucm 080499.htm

In addition to the medications listed in this table, subjects receiving venetoclax should not consume grapefruit, grapefruit products, Seville oranges (including marmalade containing Seville oranges) or Star fruits.

- * These are anticancer agents and not allowed on trial.
- ** Closely monitor the international normalized ratio (INR).
- ¹ Moderate CYP3A inhibitor per venetoclax FDA USPI.

Appendix D: Risk Assessment and Prophylaxis for Tumor Lysis Syndrome: Recommendations for Venclexta Prescribing Information

Venclexta can cause rapid reduction in tumor and thus poses a risk of TLS in the 5-week rampup phase. Changes in blood chemistries consistent with TLS that require prompt management can occur as early as 6 to 8 hours following the first dose of Venclexta and at each dose increase.

The risk of TLS is a continuum based on multiple factors, including tumor burden and comorbidities. Perform tumor burden assessments, including radiographic evaluation (e.g. CT scan), assess blood chemistry (potassium, uric acid, phosphorous, calcium, and creatinine) in all patients and correct pre-existing abnormalities prior to initiation of treatment with venetoclax. Reduced renal function (creatinine clearance < 80 ml/min) further increases the risk. The risk may decrease as tumor burden decreases.

The following table describes the recommends TLS prophylaxis and monitoring during venetoclax treatment based on tumor burden determination from clinical trial data.

Tumor Burden Categories and TLS Monitoring and Risk Mitigation Recommendations

Tumor Burden Category	Tumor Burden at start of venetoclax	Prophylaxis		Blood chemistry monitoring ^{c,d}
		Hydration ^a	Anti- hyperuricemics	Setting and Frequency of Assessments
Low	All measurable LN with the largest diameter < 5 cm by radiologic assessment AND ALC < 25 × 109/L	Oral (1.5 – 2L)	Allopurinol ^b	Outpatient - Pre-dose, 6 to 8 hours, 24 hr at first dose of 20 mg and 50 mg - Pre-dose at subsequent ramp-up doses
Medium	Any measurable LN with the largest diameter ≥ 5 cm but < 10 cm by radiologic assessment OR ALC ≥ 25 × 10 ⁹ /L	Oral (1.5 – 2L) and consider additional intravenous	Allopurinol	Outpatient - Pre-dose, 6 to 8 hours, 24 hr at first dose of 20 mg and 50 mg - Pre-dose at subsequent ramp-up doses - Consider hospitalization for patients with CrCl < 80 ml/min at first dose of 20 mg and 50 mg; see below for monitoring in hospital
High	Any measurable LN with the largest diameter ≥ 10 cm by radiologic assessment OR ALC ≥ 25 × 10 ⁹ /L AND any measurable LN with the largest diameter ≥ 5 cm	Oral (1.5 – 2L) and intravenous (150 – 200 ml/hr as tolerated)	Allopurinol; consider rasburicase if baseline uric acid is elevated	In hospital at first dose of 20 mg and 50 mg - Pre-dose, 4, 8, 12 and 24 hours Outpatient at subsequent ramp-up doses - pre-dose, 6 to 8 hours, 24 hours.

ALC = absolute lymphocyte count; LN = lymph node

^aAdminister intravenous hydration for any patient who cannot tolerate oral hydration.

^bStart allopurinol or xanthine oxidase inhibitor 2 to 3 days prior to initiation of VENCLEXTA. ^cEvaluate blood chemistries (potassium, uric acid, phosphorus, calcium, and creatinine); review in real time.

^dFor patients at risk of TLS, monitor blood chemistries at 6 to 8 hours and at 24 hours at each subsequent ramp-up dose.

Any subject, who at any dose level develops clinically significant electrolyte abnormalities, must have their subsequent venetoclax dose held until the electrolyte abnormalities resolve. Electrolyte changes should undergo aggressive management and further monitoring as per Appendix E (Recommendations for Initial Management of Electrolyte Abnormalities and Prevention of Tumor Lysis Syndrome [TLS]). The subject may resume dosing based on a risk assessment (including tumor burden status), as determined by the investigator. All subjects must receive the intended dose for at least 7 days before increasing to the next higher dose.

Appendix E: Recommendations for Initial Management of Electrolyte Abnormalities and Prevention of Tumor Lysis Syndrome (TLS)

Section 1: First Dose of Venetoclax on study or Dose Escalation

- Within the first 24 hours after either the first dose on study or dose escalation, if any laboratory criteria below are met, the patient should be hospitalized for monitoring and the investigator notified. No additional venetoclax doses should be administered until resolution. A rapidly rising serum potassium is a medical emergency.
- IV fluids (e.g., D5 1/2 normal saline) should be initiated at a rate of at least 1 mL/kg/hr rounded to the nearest 10 mL (target 150 to 200 mL/hr; not < 50 mL/hr). Modification of fluid rate should also be considered for individuals with specific medical needs.
- Monitor for symptoms or signs of TLS (e.g., fever, chills, tachycardia, nausea, vomiting, diarrhea, diaphoresis, hypotension, muscle aches, weakness, paresthesias, mental status changes, confusion and seizures). If any clinical features are observed, recheck potassium, phosphorus, uric acid, calcium and creatinine within 1 hour STAT.
- Vital signs should be taken at time of all blood draws or any intervention.
- The management recommendations below focus on the minimum initial responses required. If a diagnosis of TLS is established, ongoing intensive monitoring and multi-disciplinary management will be per institutional protocols.

In addition to the recommendations in the table below, for subjects receiving the first dose of venetoclax:

- For potassium increase ≥ 0.5 mmol/L from baseline, or any value > 5.0 mmol/L, recheck potassium, phosphorus, uric acid, calcium and creatinine within 1 hour STAT and follow first guideline.
- For phosphorus increase of > 0.5 mg/dL AND > 4.5 mg/dL, administer phosphate binder and recheck potassium, phosphorus, uric acid, calcium and creatinine within 1 hour STAT.

Abnormality	Management Recommendations	
Hyperkalemia (Including Rapid	ly Rising Potassium)	
Potassium ≥ 0.5 mmol/L increase from prior value (even if potassium within normal limits [WNL])	 Recheck potassium, phosphorus, uric acid, calcium and creatinine in 1 hour STAT. If further ≥ 0.2 mmol/L increase in potassium, but still < upper limit of normal (ULN), manage as per potassium ≥ ULN. Otherwise recheck in 1 hour. 	
	 Resume per protocol testing if change in potassium is < 0.2 mmol/L, and potassium < ULN, and no other evidence of tumor lysis. 	

Abnormality	Management Recommendations		
	 At the discretion of the investigator, may recheck prior to hospitalization. If stable or decreased, and still WNL, hospitalization is at the discretion of the investigator. Potassium, phosphorus, uric acid, calcium and creatinine must be rechecked within 24 hours. 		
Potassium > upper limit of normal	 Perform STAT ECG and commence telemetry. Nephrology (or other acute dialysis service) notification with consideration of initiating dialysis. Administer Kayexalate 60 g (or Resonium A 60 g). Administer furosemide 20 mg IV × 1. Administer calcium gluconate 100 to 200 mg/kg IV slowly if there is ECG/telemetry evidence of life-threatening arrhythmias. Recheck potassium, phosphorus, uric acid, calcium and creatinine in 1 hour STAT. If potassium < ULN 1 hour later, repeat potassium, phosphorus, uric acid, calcium and creatinine 1, 2 and 4 hrs., if no other evidence of tumor lysis. 		
Hyperkalemia (Including Rapid	ly Rising Potassium) (continued)		
Potassium ≥ 6.0 mmol/L (6.0 mEq/L) and/or symptomatic (e.g., muscle cramps, weakness, paresthesias, nausea, vomiting, diarrhea)	 Perform STAT ECG and commence telemetry. Nephrology (or other acute dialysis service) assessment with consideration of initiating dialysis. Administer Kayexalate 60 g (or Resonium A 60 g). Administer furosemide 20 mg IV × 1. Administer insulin 0.1 U/kg IV + D25 2 mL/kg IV. Administer sodium bicarbonate 1 to 2 mEq IV push. If sodium bicarbonate is used, rasburicase should not be used as this may exacerbate calcium phosphate precipitation. Administer calcium gluconate 100 to 200 mg/kg IV slowly if there is ECG/telemetry evidence of life-threatening arrhythmias. Do not administer in same IV line as sodium bicarbonate. Recheck potassium, phosphorus, uric acid, calcium and creatinine every hour STAT. 		
Hyperuricemia	·		
Uric acid ≥ 8.0 mg/dL (476 µmol/L)	 Consider rasburicase (dose based on local guidelines and/or institutional standards). If rasburicase is used, sodium bicarbonate should not be used as this may exacerbate calcium phosphate precipitation. Recheck potassium, phosphorus, uric acid, calcium and creatinine in 1 hr STAT. 		
Uric acid ≥ 10 mg/dL (595 µmol/L)	 Administer rasburicase (dose based on local guidelines and/or institutional standards). When rasburicase is used, sodium bicarbonate 		

Abnormality	Management Recommendations
OR Uric acid ≥ 8.0 mg/dL (476 µmol/L) with 25% increase and creatinine increase ≥ 0.3 mg/dL (≥ 0.027 mmol/L) from pre-dose level	 should not be used as this may exacerbate calcium phosphate precipitation. Notify nephrology (or other acute dialysis service). Recheck potassium, phosphorus, uric acid, calcium and creatinine in 1 hour STAT. If uric acid < 8.0 mg/dL 1 hour later, repeat potassium, phosphorus, uric acid, calcium and creatinine 2 and 4 hrs., later, if no other evidence of tumor lysis.
Hypocalcemia	
Calcium ≤ 7.0 mg/dL (1.75 mmol/L) AND Patient symptomatic (e.g., muscle cramps, hypotension, tetany, cardiac arrhythmias)	 Administer calcium gluconate 50 to 100 mg/kg IV slowly with ECG monitoring. Telemetry. Recheck potassium, phosphorus, uric acid, calcium and creatinine in 1 hr STAT. If calcium normalized 1 hour later, repeat potassium, phosphorus, uric acid, calcium and creatinine 2 and 4 hrs., later, if no other evidence of tumor lysis. Calculate corrected calcium and check ionized calcium if albumin low.
Hyperphosphatemia	
Phosphorus ≥ 5.0 mg/dL (1.615 mmol/L) with ≥ 0.5 mg/dL (0.16 mmol/L) increase	 Administer a phosphate binder (e.g., aluminum hydroxide, calcium carbonate, sevelamer hydroxide, or lanthanum carbonate). Nephrology (or other acute dialysis service) notification (dialysis required for phosphorus ≥ 10 mg/dL). Recheck potassium, phosphorus, uric acid, calcium and creatinine in 1 hr STAT. If phosphorus < 5.0 mg/dL 1 hour later, repeat potassium, phosphorus, uric acid, calcium and creatinine 2 and 4 hrs., later, if no other evidence of tumor lysis.
Creatinine	
Increase ≥ 25% from baseline	 Start or increase rate of IV fluids. Recheck potassium, phosphorus, uric acid, calcium and creatinine in 1 to 2 hours STAT.

Section 2: Ongoing Dosing of Venetoclax

Management of electrolyte changes from last value at intervals > 24 hours after either the first dose or dose escalation (e.g., 48 or 72 hours) are as below.

Note: If the patient is hospitalized, no additional venetoclax doses should be administered until resolution.

- For potassium, admit patient for any increase ≥ 1.0 mmol/L (1.0 mEq/L), or any level > upper limit of normal.
 - Refer to the management guidelines for electrolyte changes observed within the first 24 hours after either the first dose or dose escalation (see prior table).
- If a smaller potassium increase is observed that does not meet the criteria for admission above, recheck potassium, phosphorus, uric acid, calcium and creatinine in 24 hours and confirm no evidence of tumor lysis prior to further venetoclax dosing.
- For uric acid, calcium, phosphorus and creatinine, refer to the management guidelines for electrolyte changes observed within the first 24 hours after either the first dose or dose escalation (see prior table).

Appendix F: Venetoclax Patient Calendar for ramp-up Take VENCLEXTA tablets by mouth once daily Salar two Take two 10 mg tablets Take one 100 mg tabler Take one SO mg tabler Take two DAY 7 Take two Take one 100 mg tablet Take one 50 mg tabler M Be Man DAN'6 DAY 6 DAY 6 9 Take two Take one Take two SO mg tabled Venetoclax Ramp-Up Calendar DAYS DAY 5 9 Take two Take one 100 mg tablet Some table Take two 0 Take four 100 mg tablets Take two Take one 100 mg tablet Take one SO mg tablet Take two DAY 3 DAY 3 9 Take one 100 mg taket Take two 10 mg tablets Table one 50 mg tablet Take two Take four 100 mg tal DAY 2 DAY 2 VENCLEXTA pill bottle The medicine you will need for your 5th week of treatment and beyond is in a pill bottle. 9 WEEK 5 and beyond Take two Take one 100 mg take Mary South Company of the control of DAY 1 DAY 1 DAV ĕω throughout the day 26. if it has been less than 8 hours, take your dose as soon as possible. If it has been more than 8 hours, skip the missed dose. Take the next dose at your usual time. take your dose once a day with a meal and water at about the same time each day, Swallow each tablet whole. Do no thew, crush, or break the tablets. Write the day of the wee Prep Day 1
 Prep Day 2
 The days marked with a blue water bottle PREP DAY 2 ur healthcare provider may delay, decrease your dote, top treatment with VENCLEXTA if you have also effe your healthcare provider changes your doaling schedul in information in this calendar may no longer apply. Prep Day 1 and Prep Day 2 are the 2 days before the first dose of VENCLEXTA® (venetoclax tablets), as directed by you vomit after taking your dose, do not take an -1 Drink at least 7 cups of water water every day when taking VENCLEXTA. It is important to stay hydrated. Drink -1 How do I take VENCLEXTA? Pay special attention PREP DAY 1 =1 What if I miss my dose?
